Steps to Eliminate Postoperative Problems

v1.3 6/26/2016

PRINCIPAL INVESTIGATOR: [name] [name], MSCE (Co-PI), [name], MPH (Co-PI)

PROTOCOL TITLE: Steps to Eliminate Postoperative Problems

NCT02880176

INTRODUCTION AND PURPOSE:

Radical cystectomy with urinary diversion is associated with substantial perioperative morbidity, including deep venous thrombosis, prolonged ileus, and postoperative functional decline. Post-operative morbidity after cystectomy prolongs the length of stay, increases the risk of readmission, and adds substantially to health care costs. Protocols that emphasize early and frequent ambulation after surgery decrease post-operative morbidity, but poor patient adherence diminishes the effectiveness of these protocols, which are currently implemented only during the hospital stay. Financial incentives overcome present bias and offer a novel and practical approach to increasing ambulation during the post-operative period in the hospital and after discharge. In this application, we propose a pilot randomized, controlled trial to estimate the effect size of financial incentives on increasing post-operative ambulation in the hospital and post-discharge after radical cystectomy. Secondary outcomes include step count, composite morbidity, and functional decline. This proposal will provide the preliminary data needed to design future, larger trials that will test the effect of financial incentives to increase ambulation on post-operative complications, readmissions, and functional decline

OBJECTIVES:

In this study, we seek to determine whether financial incentives can be used as novel and practical approach to increase post-operative ambulation and thereby decrease post-operative morbidity. The primary outcome variable will be the percentage of the first 30 post-operative days on which study participants meet patient-specific ambulation goals. Secondary outcomes include 1) the number of steps taken per day, 2) composite morbidity outcome of complications, unplanned readmissions, or Emergency Department (ED) visits, and 3) functional decline as measured by the Stanford Health Assessment Questionnaire.

BACKGROUND:

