The target population is adults undergoing radical cystectomy (RC) at the Hospital of the University of Pennsylvania (HUP). 75-100 patients undergo RC at HUP each year. We anticipate recruiting and retaining 50% of eligible patients (n=46) over a one-year enrollment period. Each patient will be followed for 30 days post-operatively with the option for patients to continue submitting data for up to 90 days after their procedure. We anticipate initiating recruitment in July of 2016.

2. Key Inclusion Criteria:

1. Patient is at least 21 years old. – This excludes pediatric patients who would certainly not be representative of the general cystectomy population.
2. Patient is planned to undergo radical cystectomy at the Hospital of the University of Pennsylvania. – This is the population to which we have access for recruiting purposes.
3. Patient is ambulatory with baseline ECOG performance status less than or equal to 2. – This excludes patients for whom step counts would not be relevant or a good measure of daily activity.

3. Key Exclusion Criteria:

1. Patient is non-ambulatory or use of Fitbit to monitor activity is otherwise impossible or impractical. – See inclusion criterion #3 above.
2. Patient has a preoperative ECOG performance status of 3 or greater. – See inclusion criterion #3 above.
3. Patient knows *a priori* that he or she will be unwilling or unable to use a mobile device and online tool to upload activity data.
4. Patient is incapable of consenting for him or herself prior to surgery – Because participation in this trial involves ongoing effort on the part of the subject, we exclude patients who are incapable of consenting for themselves at baseline.
5. Patient is unable to collect step count data for at least 3 days preoperatively – Because step count goals are determined based on preoperative status, we exclude patients for whom we have insufficient preoperative step count data.

4. Subject Recruitment and Screening:

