All participants will receive education about the importance of early ambulation and knowledge of their daily step goals. Goals will be based on data collected during a lead in period during which patients' daily activity levels will be tracked to measure baseline step counts. Specifically, goals will be defined as 10%, 25%, 40%, and 55% of baseline during post-operative days 1-7, 8-14, 15-21, and 22-30 respectively. These are based on the limited experience in the literature with post-operative step-counting as well as our clinical experience with this population at HUP.⁴²⁻⁴⁵ A Fitbit Zip, a commercially available activity tracking device with the ability to record and wirelessly upload step counts, will be provided to each participant to measure the outcome of daily step counts for a lead in period of 1-2 weeks before surgery and 30 days after surgery with the option for patients to continue to submit data independently for up to 90 days after surgery. Data will be collected using the Way To Health platform, a digital platform specifically designed to facilitate randomized controlled trials testing interventions increase health-promoting behavior.

Participants will be randomized using simple balanced randomization into one of two arms: "control" or "financial incentives". Participants randomized to the financial incentives arm will receive daily payments of \$1.50 (with 100% probability)²⁶ for each day in the first 30 days after surgery that they achieve their daily step goals. Individuals will be informed if they fail to achieve adequate steps and would have otherwise been eligible for payments in order to leverage regret aversion. We chose to frame the financial incentive as a "gain" rather than a "loss"³⁰ because striving to achieve a positive reward may provide the necessary support to positively motivate patients who just had major, painful surgery.³⁴ Through a lottery, each participant who achieves 75% of the daily goals will also be eligible for a 1/5 chance of receiving \$100 at the end of the study period. We combine small definite payments with larger lottery-based payments to provide ongoing feedback coupled with the possibility of winning a higher magnitude reward. Automated notification about payments will be delivered through the participant's preferred mode of communication (e.g., phone call, email). Patients will track their earnings and step count over time through WTH.

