- The Stanford Health Assessment Questionnaire (SHAQ) is a broadly used and validated questionnaire which, in its shortened form, assesses subjects' ability to perform 20 different actions and the need for assistance with these actions. It also captures patients' global assessments of pain and well-being.³⁷ This will be administered preoperatively, 30 days post-operatively, and 90 days post-operatively to measured post-operative functional decline.
- The International Physical Activity Questionnaire (IPAQ) Short Seven Day form quantifies patient reported levels of physical activity over the seven days prior to the interview. It is similarly broadly used and has been previously validated against accelerometer data.³⁸ This will be administered preoperatively, 30 days post-operatively, and 90 days post-operatively to measure post-operative decline in physical activity and to discover differences in baseline physical activity that are not captured by preoperative step-count data.
- The Multidimensional Scale of Perceived Social Support (MPPSS) is a validated tool for assessing patient's self-assessed degree of support from others.³⁹ Prior research has suggested social support as an important factor in exercise behavior, which is consistent with our clinical observations.⁴⁰ This will be administered pre-operatively and a 30 and 90 days post-operatively to help account for confounding by this important and otherwise unmeasured variable.
- Barriers to ambulation in the hospital: Previous work has attempted to identify modifiable factors that prevent inpatient ambulation.⁴¹ Based on the factors identified in this study, we will ask participants to respond to a simple questionnaire consisting of a five-point Likert scale from "was a major barrier that prevented me from walking" to "was not a barrier that prevented me from walking". The prompts will be as follows: "Physical discomfort (e.g. pain, weakness, shortness of breath)", "Cumbersome medical devices (e.g. IVs, catheters, monitors)", "Fear of falling", "Lack of assistance from people", "Social discomfort/embarrassment", and "Lack of desire/motivation".

2. Group Modifications:

No modifications necessary.

3. Method for Assigning Subjects to Groups:

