3. If the patient is deemed eligible and has an upcoming PAT or stoma-marking appointment, the patient is met by the research coordinator after the appointment. Consent is obtained, preoperative questionnaires are administered (see schedule below), the patient is given the Fitbit device, the patient is registered with WTH, randomization occurs, and the patient is instructed on how to upload data. Data collection begins immediately and preoperative step counts are uploaded to the WTH website. Patients with ECOG performance status greater than or equal to 3 will be screened for by review of the medical record and by asking patients to select which of the first four statements in the performance status best describe them.
 - a. In the event that eligible patients are identified with no PAT or stoma-marking visit prior to surgery, the patient will be contacted by phone. Preliminary verbal consent will be obtained, questionnaires will be administered, the patient will be registered with WTH and randomized and the Fitbit device will be mailed to the patient's home. Consent is finalized in the preoperative holding area.
4. The research coordinator will monitor the data being uploaded to WTH and follow up as needed with the patient to ensure that he or she is able to begin tracking and uploading step counts.
5. Demographic information for the participant is abstracted from the medical record and recorded along with questionnaire and randomization arm in the study database.
6. On the morning of the first post-operative day, the research coordinator explains the financial reward scheme specific to the patient's randomization arm.
7. The initial \$25 compensation for participation will be written and sent upon submission of the patient's preoperative step data.
8. In the morning of each day of the hospitalization, the research coordinator assists the patient in uploading the previous day's step-count data to the Way to Health website. The website provides feedback and allocates financial rewards into a virtual wallet. During this time, the research coordinator will also assess for safety and burden on the patient as well as assisting the patient in making any preparations to transition data collection to the home setting.
9. On the day of discharge, the patient will be prompted to respond to a brief questionnaire addressing perceived barriers to ambulation in the hospital.

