10. After discharge, participants resume independently for uploading their daily step count data. The website continues to provide feedback with each upload and may be accessed *ad lib* should participants want to check their progress and rewards more frequently. Data collection continues through the 30th post-operative day.
11. On the 31st post-operative day, the WTH platform prompts the participant to fill out questionnaires according to the schedule below. On the business day following the 31st post-operative day, the research coordinator will also contact the patient to inquire about any hospitalizations, stays at skilled nursing facilities or rehab facilities, emergency room visits, or unplanned doctor visits occurred since discharge and relevant medical records will be obtained if these are not already available through the UPHS EMR. Contact information is updated as needed, and financial awards are mailed in the form of a bank check to the participant's preferred mailing address. The research coordinator will follow up with patients to ensure the questionnaires are completed.
12. Participants are allowed to continue collecting and uploading data through WTH for 90 days post-operatively, although no further financial incentives or monitoring by the research coordinator will be provided.
13. On the 91st post-operative day, the patient is prompted to fill out questionnaires according to the schedule below. This will include a brief section addressing continued personal use of the Fitbit or another personal activity tracking device. On the business day following the 90th post-operative day, the research coordinator contacts the participant by phone to screen for uncaptured complications.

The schedule for questionnaires will be as follows:

- Initial contact (PAT visit, stoma-marking visit, or phone): SHAQ20, IPAQ, MPPSS
- Day of discharge: barriers to ambulation in the hospital
- 30 day post-operative phone call: SHAQ20, IPAQ, MPPSS, screen for uncaptured complications
- 90 day post-operative phone call: SHAQ20, IPAQ, MPPSS, screen for uncaptured complications

2. Data Collection:

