This study does not involve the analysis of existing data, blood, or tissue specimens. It will involve review of the patient's University of Pennsylvania Health System electronic medical record at several points in the study. After the patient is scheduled for cystectomy, the record will undergo screening for eligibility. No data will be abstracted from the record at this point. After enrollment the chart will be reviewed again for demographic information and past medical history which will be abstracted into the research database. It may also be reviewed as necessary during the course of the study to ensure ongoing safety of participants. Finally, the record will be reviewed at the conclusion of the study to assess for complications. In the case of missing or contradictory data, the electronic medical record may be referenced to ensure the quality of collected data after the end of the study, but these reviews shall not substantially expand the scope of the data collected beyond demographic information, vitals, and past medical history present at time of study initiation.

3. Genetic Testing:

Not applicable

4. Use of Deception:

Not applicable.

5. Statistical Analysis:

We will use generalized estimating equations with participant random effects and fixed effects for time to determine the association between financial incentives and 1) achieving step goals, 2) mean number of steps taken, 3) complications, ED visits and hospital readmissions, and 4) functional decline.

As a pilot study, the proposed research will provide preliminary data (e.g. effect sizes, feasibility) needed to design larger trials that will determine the effectiveness of financial incentives to increase ambulation on decreasing post-operative complications, readmissions, and functional decline. This study was therefore not powered to detect a statistically significant difference between the groups.

RISK/BENEFIT ASSESSMENT:

1. Risks:

The primary risk is that the interventions taken in this trial result in behavioral changes that are actually deleterious to patient recovery. In theory, increased ambulation may lead to increased falls, increased pain, herniation or other wound

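### The steps-per-day model names no baseline covariate, so the comparison gives up precision, though not validity, that the lead-in step counts could supply

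*Combined protocol and SAP*

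**What the plan says.** The analysis plan is in Study Procedures, 5. Statistical Analysis. One sentence covers goal attainment, mean steps, the clinical events and functional decline with generalized estimating equations "with participant random effects and fixed effects for time". It names no covariate. The same section says that the trial is a pilot, is not powered for a group difference, and is meant to supply effect sizes for larger trials.

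Other sections bear on the point:

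- **Outcome.** Objectives: "Secondary outcomes include 1) the number of steps taken per day". The primary outcome is the share of the first 30 days on which the patient's own goal is met.
- **Baseline steps.** Study Design plans a lead-in of 1-2 weeks in which "daily activity levels will be tracked to measure baseline step counts". Key Exclusion Criteria, item 5, excludes a case where "Patient is unable to collect step count data for at least 3 days preoperatively".
- **Goals.** Study Design: "goals will be defined as 10%, 25%, 40%, and 55% of baseline" over four successive post-operative periods.
- **Order of events.** In Detailed Description, step 3, randomization takes place at the enrollment visit and step recording then starts. In step 3a, the patient is randomized and the device is mailed. Step 6: "On the morning of the first post-operative day, the research coordinator explains the financial reward scheme" that belongs to the patient's arm. Study Design says that the coordinator is unblinded.
- **Functional decline.** Study Instruments, on the Stanford questionnaire (SHAQ): "This will be administered preoperatively, 30 days post-operatively, and 90 days post-operatively to measured post-operative functional decline". The questionnaire schedule agrees: "Initial contact (PAT visit, stoma-marking visit, or phone): SHAQ20, IPAQ, MPPSS".

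**The concern.** Arm does not vary within a patient. Participant effects or a working correlation account for the clustering of days, but they leave the between-patient variation in the standard error of the arm effect. Only a between-patient predictor removes part of it, and a patient's usual daily step count is a natural one. The plan collects that value and uses it to set goals, but does not carry it into the step-count model.

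What is at stake is the width of one secondary interval. In a pilot whose product is effect-size estimates, interval width is a fair measure of the analysis. Naming the covariate in advance also removes a choice that could otherwise be made after the results are seen.

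**Working it through.** **The plan's own figure.** The sample size of 46 is an accrual forecast: half of 75 to 100 cystectomies a year is 37.5 to 50, and 46 corresponds to 92 eligible patients (0.5 x 92). The plan states no SD, correlation, power or interval width, so there is no precision figure to reproduce.

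**Inputs.** From the documents: n = 46 in two arms (taken as 23 each), 30 post-operative days, at least 3 lead-in days. Assumed: r, the correlation between the observed lead-in mean and the patient's post-operative mean, at 0.3, 0.5 and 0.7; one roughly normal covariate; all 46 analysed.

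**Unadjusted.** With complete data the arm effect is a difference between averages of patient means. In SD units of the patient mean, its standard error is sqrt(1/23 + 1/23) = sqrt(4/46) = 0.295. The 95% half-width is t(44) x 0.295 = 0.594 SD.

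**Adjusted.** The variance is multiplied by (1 - r²)(1 + 1/(n - 4)) = (1 - r²)(43/42). The factor 43/42 = 1.024 is the expected cost of estimating one coefficient. The half-width is t(43) x sqrt(4/46 x factor).

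| r | variance factor | half-width (SD) | width ratio | equivalent unadjusted n (46 / factor) |
|---|---|---|---|---|
| none | 1 | 0.594 | 1 | 46 |
| 0.3 | 0.91 x 1.024 = 0.932 | 0.574 | 0.97 | 49 |
| 0.5 | 0.75 x 1.024 = 0.768 | 0.521 | 0.88 | 60 |
| 0.7 | 0.51 x 1.024 = 0.522 | 0.430 | 0.72 | 88 |

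Break-even in variance: (1 - r²)(43/42) = 1 gives r = sqrt(1/43) = 0.152.

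**Short lead-in.** A noisy baseline lowers r, so this loss is already inside the table. To show its size, participant means were simulated with day-to-day SD assumed equal to between-patient SD (4,000 trials per case). For underlying person-level correlations of 0.3, 0.5 and 0.7, the standard-error ratio was 0.97, 0.91 and 0.81 with 3 lead-in days, and 0.98, 0.88 and 0.76 with 10. The two values at 0.3 differ only by simulation error.

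**Repeated-day structure.** A GEE simulation (2,000 trials per case; 23 per arm; 30 days; exchangeable working correlation; day effects; assumed between-patient and day-to-day SD of 0.9 each, AR(1) 0.5) gave these standard-error ratios, adjusted to unadjusted:

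| r | complete data | 10% of days missing, 15% of patients stopping early |
|---|---|---|
| 0 | 1.008 | 1.013 |
| 0.3 | 0.966 | 0.965 |
| 0.5 | 0.877 | 0.883 |
| 0.7 | 0.734 | 0.737 |

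This agrees with the closed form. Since r is an input, it confirms the formula and not the value of r. The worst entry, 1.013² = 1.026, is why the cost is given as about 2-3% and not as a strict bound.

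**SHAQ, if analysed as a continuous score.** Let k be the post-operative SD divided by the pre-operative SD. The variance of the baseline-adjusted analysis relative to a change score is k²(1 - r²)(43/42) / (k² + 1 - 2rk):

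| k | r = 0.3 | r = 0.5 | r = 0.7 |
|---|---|---|---|
| 0.7 | 0.43 | 0.48 | 0.50 |
| 1.0 | 0.67 | 0.77 | 0.87 |
| 1.25 | 0.80 | 0.91 | 1.00 |
| 1.5 | 0.89 | 0.99 | 1.02 |

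**The case against.** **No error is shown, and r may be low.** The unadjusted comparison is valid, the outcome is secondary and the trial is declared unpowered. Goals of 10% to 55% of baseline imply that steps will be well below usual for the whole period, and the Background names pain, opioid lethargy and poor motivation as barriers. Early post-operative walking may therefore follow usual walking only loosely. At r = 0.3 the gain is about 3% in width. This stands as a limit on size. It does not remove the point, because the pilot exists to estimate effects and the expected cost of being wrong is small.

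**The covariate is measured after randomization.** The unblinded coordinator is in contact with patients during the lead-in (Detailed Description, step 4). If lead-in steps came to differ by arm, adjusting for them could add bias. The 3-day criterion can also be checked only after randomization, so some randomized patients may lack the value. Both parts stand and shape the fix. Disclosing the scheme only on post-operative day 1 limits the first risk but does not abolish it.

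**The investigators did think about baseline.** Study Instruments collects the social support scale to deal with confounding, and the IPAQ to find activity differences that pre-operative steps miss. A reader might infer that baseline was ignored; the documents do not support that. The gap is that the intent is not carried into the model. Lead-in days might also be meant as outcome rows with an arm-by-time term, which would use baseline, but the plan does not say so.

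**Functional decline.** The word decline already suggests that the pre-operative SHAQ enters somehow. A reader might infer a sure loss of precision here too. That is not supported: the main gap is that the endpoint is undefined.

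**Conclusion.** The point holds as a suggestion about efficiency on steps per day. Adjustment for lead-in steps would multiply the 95% interval width by about 0.97, 0.88 or 0.72 at r = 0.3, 0.5 or 0.7. It does slightly worse than no adjustment below r of about 0.15, with an expected variance cost of about 2-3% if baseline carries no information. These figures rest on an assumed r, 46 analysed patients and an approximately normal, linear covariate.

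Two stronger readings should be resisted. A reader might infer that the planned comparison is biased; randomization makes it valid, and the loss is in precision only. A reader might also extend the gain to the primary outcome; its goals are already scaled to each patient's baseline, and no gain is claimed there. For SHAQ the point is secondary and conditional: against a change score, the gain runs from substantial to none.

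**What to change.** Add to the Statistical Analysis section:

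1. **Covariate.** Mean lead-in daily steps enters the step-count model on one stated scale, the same as the outcome's (raw with raw, or log with log).
2. **Safeguards for a covariate measured after randomization.** State that the arm-specific scheme stays undisclosed until post-operative day 1, as step 6 already has it. Report lead-in steps by arm, and give the unadjusted estimate as a sensitivity analysis.
3. **Missing baseline.** State a rule for randomized patients with few or no lead-in days, for example to use all available days and otherwise impute the overall baseline mean pooled across arms.
4. **Functional decline.** Define it. If it is a continuous SHAQ score, analyse day-30 and day-90 SHAQ adjusted for pre-operative SHAQ. This also fixes which effect size goes forward to the next trial.

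The cost is a few sentences and one estimated coefficient per model. No new data and no added patient burden are involved.

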complications, etc. None of these outcomes would be consistent with current literature and are therefore considered highly unlikely.⁴⁻¹⁰ It is also possible that patients respond paradoxically to financial incentives or biometric monitoring and perform fewer of the desired behaviors. Finally, the psychological impact of our behavioral tools is incompletely understood: while subjects in other studies usually report finding financial incentives to be positively motivating and even empowering, failure to achieve objectives may lead to feelings of guilt or shame. Overall the risk of participation is considered low.

2. Benefits:

The primary goal of the randomized portion of the study is to develop strategies to motivate patients to increase behaviors that are beneficial to their post-surgical recovery in the short term. The benefits of post-operative early ambulation are well documented and include decreased risk of serious complications such as venous thromboembolism (e.g. deep venous thrombosis, pulmonary embolism), pneumonia, and post-operative deconditioning. Participation in the study alone is likely to increase ambulation via a Hawthorne effect, and a subset of patients will further receive direct financial benefit for engaging in this beneficial behavior.

3. Subject Privacy:

Subject privacy will be maintained by limiting subject-researcher interaction to settings which are already deemed appropriate for clinical interactions, namely outpatient clinics, telephone conversations, the preoperative holding bay, and hospital rooms. The Way to Health website is also specifically designed to allow for confidential upload of information. Step counts, a novel piece of data about subjects which would not otherwise be recorded, will be exposed only to the patient, the research coordinator, and the Way to Health website unless the patient chooses to share that information with others.

4. Subject Confidentiality:

How will confidentiality of data be maintained? Check all that apply.

- Paper-based records will be kept in a secure location and only be accessible to personnel involved in the study.
- Computer-based files will only be made available to personnel involved in the study through the use of access privileges and passwords.
- Prior to access to any study-related information, personnel will be required to sign statements agreeing to protect the security and confidentiality of identifiable information.

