Patients participating in the study will initially be subject to the intensive monitoring of the post-operative acute care hospital setting. Safety issues caused by the study are very likely to be detected early in this environment. [name] is already highly involved in the care of these patients, and as the principal investigator responsible for clinical implementation, he will be immediately available to the staff who may report safety issues that arise during study implementation. Safety issues may also be detected by or reported to the research coordinator who will see the participants daily during their hospitalization. Given the relatively small sample sizes, no interim analyses are planned, however data will be assessed for quality on a continuous basis.

8. Investigator's Risk/Benefit Assessment:

The benefits of participation in this study dramatically outweigh the risks from both the perspective of the individual participant and from the perspective of the cystectomy patient population in general. Participants are likely to be motivated to engage in activities that will prevent major complications and speed recovery at the cost of minimal inconvenience, risk of breach of privacy, and possible psychological stress.

INFORMED CONSENT:

1. Consent Process:

Eligible patients will be approached following their PAT or stoma-marking visit. A medical interpreter will be used if such was deemed necessary during the patient's clinical visit. The research coordinator will identify him or herself as an employee of the University of Pennsylvania working with the Division of Urology on research to promote improved surgical outcomes in patients undergoing radical cystectomy. It will be emphasized that participation is entirely voluntary and that declining enrollment will not have any other effects on the patient's clinical care. The patient will be given the opportunity to ask questions and informed consent will be obtained. Consenting participants will respond to questionnaires, will be given the Fitbit, will be enrolled in WTH, and will be instructed on the use of the device.

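### Falls are the first-named example of the primary risk, but no falls item is specified, so falls at home that do not lead to care may be missed or asked about differently by arm.

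*Combined protocol and SAP*

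**What the plan says.** **The risk.** RISK/BENEFIT ASSESSMENT, 1. Risks, gives as the primary risk that the intervention changes behaviour in a way that harms recovery. Its first example is falls: "increased ambulation may lead to increased falls, increased pain, herniation or other wound" complications. The same section then plays this down: "None of these outcomes would be consistent with current literature and are therefore considered highly unlikely".

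**The goals.** STUDY DESIGN sets them for all participants: "goals will be defined as 10%, 25%, 40%, and 55% of baseline during post-operative days 1-7, 8-14, 15-21, and 22-30 respectively".

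**Safety in hospital.** In STUDY PROCEDURES, 1. Detailed Description, step 8, the coordinator assesses safety each morning of the stay. RISK/BENEFIT ASSESSMENT, 7. Data and Safety Monitoring, relies on the acute-care setting: "Safety issues caused by the study are very likely to be detected early in this environment".

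**After discharge.** Participants upload step counts on their own. The coordinator calls before day 31 only if uploads lapse (Early Withdrawal of Subjects; METHODS, 6. Subject Follow-up). At day 31 (step 11) the coordinator is to "inquire about any hospitalizations, stays at skilled nursing facilities or rehab facilities, emergency room visits, or unplanned doctor visits occurred since discharge". The questionnaire schedule adds a screen to the same call: "30 day post-operative phone call: SHAQ20, IPAQ, MPPSS, screen for uncaptured complications". At 90 days (step 13), "the research coordinator contacts the participant by phone to screen for uncaptured complications". METHODS, 4, explains that both calls look for complications that the health system's own record would not hold.

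**What is recorded.** The composite secondary outcome includes complications, but the term is not defined. The only other mention of falling is an item at discharge on whether worry about falling was a barrier to walking. It does not count falls.

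**The concern.** The trial pays one arm to walk more after major surgery and names falls as the first way in which this could do harm. The post-discharge part of the plan, where the goals peak, contains no instruction to ask about falls. The one open-ended element, the complications screen, is left to the coordinator, who STUDY DESIGN says is unblinded.

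Two things are at stake. A fall that the participant handles at home leaves no entry for the end-of-study chart review, and a coordinator need not regard it as a complication. If the screen is improvised, the arms may also be questioned with different thoroughness, and the resulting counts would not be comparable. The pilot is meant to supply preliminary data for larger trials, and an arm-level count of this harm belongs among those data.

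**Working it through.** The plan states no figure on this point, so there is none to reproduce. The check compares the sections and adds three short calculations.

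**1. Would a fall at home be recorded?**

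| Type of fall | Route in the plan | Found? |
|---|---|---|
| Leads to admission, facility stay, ED visit or unplanned doctor visit | Step 11 question, records obtained, chart review | Should come to light |
| No care sought | Complications screen, content not stated | Depends on what the coordinator asks and what the participant counts as a complication |

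The gap is the second row.

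**2. When do the goals peak relative to discharge?** Inputs: the four goal bands in STUDY DESIGN. Weight each band by its number of days:

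- Days 1-7: 7 × 10 = 70
- Days 8-14: 7 × 25 = 175
- Days 15-21: 7 × 40 = 280
- Days 22-30: 9 × 55 = 495
- Sum: 1,020

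Days 22-30 are 9/30 = 30% of the days and 495/1,020 = 48.5% of the summed goal. They lie wholly after discharge for any stay under 22 days. The documents give no length of stay, so the rest is shown over an assumed range:

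| Assumed last hospital day | Post-discharge days | Share of summed goal after discharge |
|---|---|---|
| 5 | 25/30 = 83% | (1,020 − 50)/1,020 = 95% |
| 10 | 20/30 = 67% | (1,020 − 70 − 75)/1,020 = 86% |
| 14 | 16/30 = 53% | (1,020 − 70 − 175)/1,020 = 76% |

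These shares describe where the goals fall in time. They do not measure fall risk.

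**3. What could a falls count show?** Input: n = 46 (Target Population and Accrual). Equal arms are assumed, so 46/2 = 23 per arm.

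- Zero fallers in an arm: one-sided 95% upper bound = 1 − 0.05^(1/23) = 12.2%. The upper limit of a two-sided 95% interval is 1 − 0.025^(1/23) = 14.8%.
- Chance of at least one faller in an arm = 1 − (1 − p)^23. The documents give no fall rate. For assumed 30-day risks p of 2%, 5% and 10%, the chance is 37%, 69% and 91%.

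A falls item would thus often yield some events to describe, but it could not exclude a moderate risk or compare the arms with any precision.

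**The case against.** The strongest reply is that both calls already carry a screen aimed at events missing from the record, so the mechanism exists and only its detail is absent. Much of this stands. A reader might infer from step 11 that the calls ask about health-care use alone, that every fall at home goes unrecorded, or that the plan cannot report on its named harm at all. The documents do not support any of these. The screen is in the schedule at both time points, falls that lead to care would surface through step 11, and the screen might pick up others. Wound problems and hernias are naturally read as post-operative complications, which the plan already seeks, and the SHAQ captures overall pain. The gap is therefore specific to falls without care.

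The plan also has other routes for safety information after discharge: chart review as needed, contact after a 24-hour upload lapse, and a phone number and email address for the coordinator. None of these asks about falls.

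Two further inferences fail. The goals follow the post-operative day and not the location, so the in-hospital goal is 10% of baseline only through day 7. And 55/10 = 5.5 is a ratio of goals that apply to both arms; it says nothing about fall risk or a difference between arms.

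The reply does not fill the gap itself. The screen has no wording, the person conducting it knows the arm, and an unattended fall leaves nothing for chart review to find. Rating the harm as highly unlikely is an expectation that the trial could check at little cost.

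**Conclusion.** The concern holds in a limited form. The plan names falls first under its primary risk, specifies no falls item, and leaves the post-discharge screen undefined in the hands of an unblinded coordinator. Falls at home without care may be missed or ascertained unequally by arm, in a period that includes the highest goals for any stay under 22 days.

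How many falls this involves cannot be estimated from the documents, which give neither a fall rate nor a length of stay. It would go too far to say that the trial must support its risk/benefit statement with a falls comparison. That statement is an advance assessment, the pilot is declared unpowered, and 23 per arm would leave an upper bound near 12% even with no fallers. This is a worthwhile, inexpensive improvement in harms collection. It does not threaten the primary outcome.

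**What to change.** Write a short script for the complications screen at the existing 30- and 90-day contacts, with identical wording in both arms:

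- Any fall since discharge (at 90 days: since the last contact), whether or not care was sought.
- If yes, how many, and whether any caused injury.
- Optionally, any new wound opening or bulge, within the same screen.

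Report by arm the number of participants asked, the number with at least one fall, total falls and injurious falls. Keep the two windows separate, because incentives stop at day 30. Present these descriptively with exact intervals and without a hypothesis test.

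The cost is two or three questions on calls already planned and one safety table. The downside is slightly longer calls and some recall error over a month or more. Fixed wording reduces the scope for questioning to differ by arm but does not remove the coordinator's knowledge of the assignment.
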